7.0 Study Withdrawal/Discontinuation

We will emphasize in our informed consent that participation is completely voluntary and that participants can excuse themselves from the study at any time with no negative repercussions.

8.0 Statistical Considerations

The sample size of 110 for the RCT is based on our Phase 1 pretest results and an a priori power analysis for a multiple regression with 4 predictors of PrEP adherence, which was conducted to determine a sample size with a power of at least 90% with a two-sided alpha level of .05. The desired minimum sample size was 92 participants (Rosner, 2010). In the event of 20% attrition, we added 20% additional participants to the sample, and set 110 as the total sample size. Therefore, even if the study encounters diminished recruitment or greater post-recruitment attrition, it should still be possible to detect moderate effects.

9.0 Privacy/Confidentiality Issues

The research study will be monitored by the research team and the Pearl IRB. All study staff (PI, project manager, research assistant, consultants) will have completed human subjects training. Although the RCT study will be implemented online, the team will nevertheless review RCT data collected via Qualtrics for accuracy and safety. All data collected will have patient identifiers removed. No reports or papers based on the project will use any individual level data or include participant names or identifying information.

All study procedures (formative and RCT) will be reviewed by Pearl IRB. Only aggregate level deidentified data will be transferred between sites and/or aggregated on-site, with any data stored on secure servers and transmitted via secure protocols, encrypted email, password-protected media, and other appropriate protections.

10.0 Follow-up and Record Retention

Informed consent documents and a master list linking the participants' names to their number will be kept in a password-protected computer, separate from other study documents. Only the PI and study staff have access to these data. All participant data gathered via the HIPAA-compliant Qualtrics platform will be removed from Qualtrics at study conclusion and stored in a secure, encrypted drive on an EHG computer. These measures are outlined in the RCT informed consent.

Analysis plan:

Data Analysis: Analyses will be performed using SPSS version 22 to run diagnostics (tests for normality, multicollinearity, heteroscedasticity) to assess violations of analytic assumptions, univariate statistics, bivariate tests, and multivariate linear regression. Because study retention may be influenced by preconditions, t-tests or Wilcoxon test will be used to compare intervention group and control group on all T1 variables. T- tests can be used for normal distribution while Wilcoxon test can be used in skewed distribution. Implications of significant differences will be discussed. Based on the intent to treat approach, missing T2 data will be imputed to retain all participants in analyses. We will include all participants who provide informed consent and engage in the T1 assessment, regardless of what portion of the assigned treatment or control protocol is completed. Data will be imputed using multiple imputation for participants who fail to complete the T2 (posttest) assessment.

Sensitivity analyses will explore the implications of the imputation methods employed (e.g., multiple imputation, propensity score matching). Post- recruitment attrition (loss of potential participants who were recruited but failed to engage in any assessments or part of the treatment or control protocol) will be explored in all discussion and implications of study findings. The following series of regressions will assess study hypotheses.

Hypothesis 1: Exposure to mhealth intervention will result in significant improvement in PrEP adherence compared to the control group. We will firstly examine the distribution of all variables and their correlations. Where two similar variables are correlated at $r>0.4$, 1 variable will be selected for inclusion in regression models to avoid collinearity (see Patel et al., 2016). We will employ multivariate linear regression to estimate the association between the intervention and PrEP adherence. In order to compare the difference of PrEP adherence (after 12 weeks) between intervention group and control group, the first regression model will only include the dichotomous treatment variable (intervention group versus control). Based on the first model, the second regression model will add three confounders (three demographic variables: age, education, and income) to compare the gaps after controlling for age, education and income level. Based on the second model, besides the 3 confounders, the third regression model will add an interaction term, the dichotomous treatment variable and the dichotomous intervention variable (before the intervention vs after) and their interaction. The coefficient of the interaction term will be the difference between the increase in intervention group and the increase in control group.

Hypothesis 2: The impact of intervention on the primary outcome will be mediated through key factors, i.e. increased PrEP self-efficacy, increased PrEP knowledge, increased intention to follow PrEP guidelines, and reduced stress burden. To test

the mediation effect, the following three regressions will be conducted. First, we will set PrEP adherence as the dependent variable, demographic variables and dichotomous treatment variable and other independent variables as the independent variables. Second, we will set PrEP adherence as the dependent variable, and each of the four mediators as the independent variable. Third, we will set the dichotomous treatment variable as the dependent variable and each of the four mediators as the independent variables. The coefficients of the three regressions will show the mediation effects. Time on PrEP will be examined as a potential moderating variable, including the potential for moderated mediation in which mediators may become significant only at certain levels of the time since starting PrEP. Results will be interpreted via the standard interpretation of a sequence of regression models (Aneshensel, 2002; Baron & Kenny, 1986) to determine whether these variables mediate or partially mediate intervention effects, and the extent to which time on PrEP moderates these relationships.

Measures. Both baseline (T1) and 12-week follow up (T2) data will be collected on the following key measures: **Primary outcome measure:** The primary outcome compares differences between (T1) and (T2) for the key measure of interest: PrEP adherence: Our Phase 1 open-ended data revealed participants' general discomfort with blood tests and needles. Thus, we will not seek PrEP blood levels in Phase 2 to measure adherence as doing so would likely pose a barrier to recruitment and retention. Instead, we will use Wilson's simple 3-item self-report adherence measure which showed good psychometric characteristics and good construct validity when compared with an electronic drug monitoring standard, for both HIV and non-HIV medications, and has been validated with culturally-diverse patient groups, including MSM (Fowler et al., 2014; Wilson et al., 2014; 2016). The items include: 1) In the last 30 days, on how many days did you miss at least one dose of any of PrEP (write in # of days) 2) In the last 30 days, how good a job did you do at taking your PrEP in the way you were supposed to? (6-point Likert) 3) In the last 30 days, how often did you take your PrEP in the way you were supposed to? (6-point Likert). Note: We will also examine self-report app adherence data. App adherence data can only be collected via the app as yes or no responses to pill reminders, and thus cannot serve as pre-intervention baseline. We will, however, compare app adherence data from weeks 1 and 12.

Consideration of Relevant Biological Variables: We will only include culturally-diverse young adult males who have sex with other males in our study as they are disproportionately represented among groups at increased risk for HIV. Moreover, males account for 95.3% of all PrEP users (Huang et al., 2018).

Mediating Variables: We propose four mediating variables: PrEP self-efficacy, intention to follow PrEP guidelines, PrEP knowledge and stress burden. To measure PrEP treatment self-efficacy, we will use the **Adherence Self-Efficacy Scale** (ASES) (Johnson et al., 2007). It is a 12-item scale of patients' confidence to carry out

important HIV treatment-related behaviors, most of which overlap with PrEP behaviors ([name], personal communication, 2019), including taking medication in face of barriers (e.g., How confident are you that you can stick to your medication when your daily routine is disrupted?). [name] made slight modifications to the ASES for use with PrEP. We include **intention to follow guidelines** as a mediator because we believe that intending to follow guidelines reflects greater “patient activation” (see Hibbard & Greene, 2013), which is associated with better medication adherence. Furthermore, showing up for 3-month testing, in itself, increases patients’ interactions with providers, which can also positively impact adherence (see Chen et al., 2013).

Because there were no measures for **intention to follow PrEP guidelines**, Drs. [name] and [name] created a 5-item measure informed by a 2-item measure of safe sex intentions developed by Fischer et al. (1998) for use with MSM. A sample item from the new measure includes: While I’m on PrEP, I intend to be tested for HIV and STDs every 3 months (5-point Likert ranging from very untrue to very true). There are also no PrEP knowledge measures. Therefore, Drs. [name] and [name] created a **6-item multiple-choice instrument** with face validity based on the Truvada patient education booklet and CDC guidelines. Content covers PrEP knowledge (medication purpose, side effects, concomitant condom use, HIV testing), all of which will be covered in educational texts.

Sample item: If you take PrEP, you should use condoms: a) every time you have anal intercourse b) most times you have anal intercourse c) only if you have anal intercourse with a HIV+ partner d) you don't need to use condoms if you are on PrEP (correct answer: a). Because our Phase 2 study is twice the length of Phase 1, participants will receive twice as many PrEP education texts. Thus, we still expect to see PrEP knowledge improvement in Phase 2, despite lack of change in Phase 1.

Perceived stress burden will be included as a potential mediating variable for two reasons: First, the intervention targets stress burden via supportive texts and an online community. Second, reductions in perceived stress can facilitate medication adherence (Stewart et al., 2005). Stress burden will be assessed using the 10-item **Perceived Stress Scale** (Cohen et al., 1983), which has been validated with a wide-range of patient and non-patient groups (e.g. Chiu et al., 2016; Perera et al., 2017). We will analyze psychometric properties and construct validity on the two new measures (intention to follow guidelines and PrEP knowledge) as a part of our Phase 2 analyses.

Moderating Variable. Length of time on PrEP (in months) will be included as a moderator as it seems possible that the greater the length of time on PrEP, the more likely a participant has developed personal strategies to support adherence or have supports (family members, friends, healthcare providers) in his social environment that help with adherence.

Demographic and Control Variables. T1 assessments will also gather a number of demographic indicators, including age, years of education, income and, as mentioned above, length of time on PrEP. Income will be coded categorically from 1 to 7 in relation to the federal poverty level: <100% (1), 100%-149% (2),

150%-199% (3), 200%-249% (4), 250%-299% (5),
300%-349% (6), 350%-399% (7), and $\geq 400\%$.

Randomization: Participants will be randomly assigned to intervention or control group via the randomizer function on Qualtrics software. **Sample size:** We will aim to recruit and gain consent from 110 participants (55 each for intervention and control arms). **Power analysis:** Based on our Phase 1 pretest results, an a priori power analysis for a multiple regression with 4 predictors of PrEP adherence was conducted to determine a sample size with a power of at least 90% with a two-sided alpha level of .05. The desired minimum sample size was 92 participants (Rosner, 2010). In the event of 20% attrition, we added 20% additional participants to the sample, and set 110 as the total sample size. Therefore, even if the study encounters diminished recruitment or greater post-recruitment attrition, it should still be possible to detect moderate effects.

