5.0 Study Procedures

The proposed study will include 2 zoom focus groups of 6-8 individuals each (or zoom interviews with the same number of individuals), which will solicit feedback on text messages and the usability of the prototype app and be approximately 2 hours long, and a randomized control trial (RCT) to evaluate the effectiveness of the DOT intervention on PrEP adherence among young adult MSM on PrEP. For the RCT, those who meet study criteria will complete online baselines in Qualtrics, then be randomized by Qualtrics to either the intervention group (DOT mobile app) or the control group (2page document offering PrEP adherence education).

Study procedures:

Formative Focus Groups/Interviews: After signing an online informed consent form, individuals will meet together for a 2 hour conversation (either in a focus group or interview), during which they will provide feedback on new text messages and the usability of the prototype app. Focus groups will be audiotaped. Participants will receive a \$75 Amazon gift card at the end of the focus group.

RCT (both arms): Those who consent to the RCT will automatically receive a link to collect demographic data, e.g. age, ethnicity, education, income, and length of time on PrEP, and the baseline assessments. Qualtrics will then randomize participants to the intervention or control arm. Intervention and control participants will be offered a \$20 Amazon gift card for completing baselines. At study completion (12 weeks), all participants will receive a text and email informing them that it is time to re-take baseline assessments. After completion, they will receive a \$155 Amazon gift card.

RCT Intervention Group: Intervention participants will receive a link to download the DOT mobile app from our website. During the 12-week study period, intervention participants will receive 3 types of messages: pill reminders, educational, and motivational (including new ones targeting stress). The

Protocol #2 R44 MH112221-02

Version: 3

November 23, 2020

DOT app will also include a link to the DOT online community (with online community rules that each participant must agree to before become a part of the community) and a “GET HELP NOW” link to the federal crisis intervention program. We have attached the online community rules for IRB review.

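### The SAP's retention check compares the randomised arms, not T2 completers with non-completers, and no named sensitivity analysis varies the missing-data assumption

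*SAP*

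**What the plan says.** The SAP's Data Analysis section gives retention as the reason for its T1 tests: "study retention may be influenced by preconditions, t-tests or Wilcoxon test will be used to compare intervention group and control group" on all T1 variables, with significant differences to be discussed. Protocol section 5.0 sets the order of events: "those who meet study criteria will complete online baselines in Qualtrics, then be randomized by Qualtrics to either the intervention group" or the control group.

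For missing T2 data the SAP states: "Data will be imputed using multiple imputation for participants who fail to complete the T2 (posttest) assessment". Everyone who consents and engages in T1 stays in the analysis. Sensitivity analyses will "explore the implications of the imputation methods employed (e.g., multiple imputation, propensity score matching").

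One further sentence deals with attrition, defined as "loss of potential participants who were recruited but failed to engage in any assessments or part of the treatment or control protocol". This "will be explored in all discussion and implications of study findings".

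On sample size, the SAP's power paragraph says "The desired minimum sample size was 92 participants" and "In the event of 20% attrition, we added 20% additional participants to the sample", giving 110. Protocol section 8.0 gives the same figures.

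**The concern.** The stated purpose and the specified test do not match. T1 comes before randomisation, so an arm difference at T1 among all participants is chance. The SAP does not restrict the test to T2 completers. If it did, the test could detect only loss that differs between arms; loss of poor adherers from both arms alike would remain invisible.

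Nothing else in either document fills the gap. No comparison of T2 completers with non-completers is specified, and no tabulation of T2 attrition by arm. The attrition sentence, on its natural reading, concerns recruits who never engaged, and it promises exploration in the discussion without naming an analysis.

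The sensitivity analyses leave a second gap. Multiple imputation is already the main method. As ordinarily used, both it and propensity score matching rely on observed data to explain dropout, so switching between them does not test that assumption.

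The outcome is self-reported adherence. If the planned 20% attrition occurs between T1 and T2, about one in five T2 values will be imputed. To judge the imputation, a reader needs to know whether those lost had lower T1 adherence, whether losses differed by arm, and whether Hypothesis 1 survives if non-completers adhere worse than similar people who stayed.

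**Working it through.** **1. The plan's own figure.** 92 × 1.20 = 110.4, which reproduces 110 (55 per arm). At 20% loss, 110 × 0.80 = 88 complete T2 and 22 do not. If the loss is equal across arms, that is 44 and 11 per arm.

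**2. Which test can detect selective loss?** The documents give no effect size, T1–T2 correlation or arm-specific attrition, so these inputs are assumed: 55 per arm, 20% dropout, and a logit slope for dropout of 0.5 or 0.8 per SD of T1 adherence. When selection acts in both arms, dropouts are then 0.48 or 0.73 SD lower at T1. Rejection rates at two-sided 0.05 (4000 runs; 6000 for the within-arm row):

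| Selection | Test on T1 adherence | Slope 0.5 | Slope 0.8 |
|---|---|---|---|
| Both arms | Arms, everyone | 4.9% | 5.4% |
| Both arms | Arms, T2 completers only | 5.5% | 5.4% |
| Both arms | Completers vs non-completers | 52.6% | 87.7% |
| App arm only | Arms, everyone | 4.8% | 4.3% |
| App arm only | Arms, T2 completers only | 7.1% | 9.8% |
| App arm only | Completers vs non-completers, app arm | 28.9% | 58.8% |

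On everyone, the arm comparison stays at its null rate throughout. Restricted to completers, it gains little even when only one arm loses people selectively.

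**3. Precision of the better comparison.** By the two-sample t-test, 80% power needs a difference of about 0.67 SD for 22 versus 88, and about 0.96 SD for 11 versus 44 within an arm. A p-value alone would therefore be a weak summary.

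**4. Effect of wrong imputed values.** Let f be the fraction missing in an arm and δ the amount, in SD, by which true T2 adherence falls below the imputed values.

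Change in (app − control) = f_control × δ_control − f_app × δ_app, with f = 11/55 = 0.20.

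- δ = 1 in the app arm only: −0.20 SD
- δ = 1 in the control arm only: +0.20 SD
- δ = 1 in both arms: 0

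**5. Shift that removes significance in Hypothesis 1, model 1 (treatment only).** With 44 observed per arm, SE ≈ √(2/44) = 0.213 SD. The app-arm shift at which significance is lost is (d − 1.99 × 0.213)/0.20.

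- d = 0.50: (0.50 − 0.424)/0.20 = 0.38 SD
- d = 0.68: (0.68 − 0.424)/0.20 = 1.28 SD

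The value 0.68 is back-solved. If N = 92 gives 90% power for the treatment coefficient in a four-predictor regression (87 residual df), f² = 0.117 and d = 2√0.117 = 0.68. If N = 92 is instead for the overall four-predictor test, f² = 0.177, which implies no particular treatment effect. The value 0.50 is an assumption; it has 66% power at N = 92.

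A delta-adjusted imputation simulation (500 runs, 20 imputations, T1 in the imputation model, assumed T1–T2 correlation 0 or 0.5) gave 0.34 and 0.40 SD for d = 0.50, and 1.16 and 1.22 SD for d = 0.68. Both agree with the closed form.

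**The case against.** The strongest objection concerns the word attrition. Protocol section 8.0 and the SAP's power paragraph both mention post-recruitment attrition alongside the 20% allowance. If the 20% means recruits who never engage, they have no T1, fall outside the analysis set and are never imputed, so the imputed share could be well below one in five. If it includes loss by T2, the SAP's promise to explore attrition may cover that loss too. The ambiguity is real, and it makes the one-in-five figure conditional. It does not supply the missing analysis, because on either reading no comparison is specified.

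The arm comparison also has some relevance. If preconditions affect retention, a chance T1 imbalance could lead to different losses by arm. That supports keeping the baseline table; it does not turn it into a check on who was lost.

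The sensitivity list is open, so a departure from the usual assumption is not ruled out. But none is named, and delta adjustment is one option among several.

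Finally, the magnitudes rest on assumed inputs, equal errors in both arms cancel, and at 0.68 SD it takes a large one-arm error to overturn the result. The significance-loss shifts were worked out for model 1 only, not for the interaction in model 3, which estimates the T1-to-T2 change that the SAP calls the primary outcome. The completer comparison is descriptive and cannot prove the missing-data assumption. All of this stands as a limit on size; none of it removes the omission.

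**Conclusion.** The concern holds. The test specified does not serve the purpose given for it, no comparison of T2 completers with non-completers is planned, and no named sensitivity analysis varies the assumption about missing data.

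The consequence depends on facts the documents do not give. Under the assumed selection, the planned test detects nothing beyond its false-positive rate. With 20% missing per arm, an app-arm error of about 0.3 to 0.4 SD would remove significance for a 0.5 SD effect, and about 1.2 to 1.3 SD for a 0.68 SD effect. Hypothesis 1 could thus be fragile or robust, and the plan names no analysis to show which. This is no evidence of bias. The change should be made because it is cheap and the SAP itself raises retention as a concern.

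**What to change.** 1. Keep the T1 table by arm as baseline description. Make the retention check a comparison of T2 completers with non-completers on the T1 variables, including adherence and time on PrEP, overall and within each arm. Report T2 attrition by arm. Give standardised differences with confidence intervals rather than p-values alone.
2. State that the imputation model includes arm, T1 adherence and the predictors of dropout.
3. Name delta-adjusted multiple imputation as a sensitivity analysis for Hypothesis 1. Shift imputed T2 adherence in each arm separately over a prespecified range, for example 0 to 1.5 SD worse (a suggestion, not a figure from the documents), and report the shift, if any, at which the conclusion changes.
4. Say whether the 20% allowance means loss before T1, between T1 and T2, or both.

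The cost is SAP wording and a few hours of analysis on data already collected. The downside is one more table and a sensitivity result that may be less favourable.

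### T2 asks 36 items but the primary outcome needs only three, and no three-item fallback is planned before imputation

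*SAP*

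**What the plan says.** The SAP (Measures) takes as primary outcome a "simple 3-item self-report adherence measure", with each item looking back over the last 30 days. The same part of the SAP collects four mediator scales at both time points: self-efficacy, intention to follow guidelines, PrEP knowledge and perceived stress.

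Protocol Section 5.0 (RCT, both arms) says that at 12 weeks "all participants will receive a text and email informing them that it is time to re-take baseline assessments". A $155 gift card follows completion. No reminder, question order, payment for a partial T2 or shortened version is described.

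The SAP (Data Analysis) keeps in the analysis everyone who consents and takes part in T1, however much of the assigned protocol he goes on to complete. It says first that missing T2 data will be imputed, and then: "Data will be imputed using multiple imputation for participants who fail to complete the T2 (posttest) assessment". It does not define a partly completed T2. Sensitivity analyses are to explore the imputation method, with multiple imputation and propensity score matching as examples.

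The sample size text (Protocol Section 8.0 and SAP, Power analysis) gives a minimum of 92, a 20% allowance for attrition and a total of 110.

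**The concern.** The plan goes from one request for the whole battery straight to imputation. A man who will not work through all the scales might still answer three short questions, and those three are all that the primary outcome needs. As written, nobody asks him for them separately.

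An imputed outcome rests on an assumption that the trial cannot check: that men without T2 resemble men with T2 who share their recorded characteristics. This matters for an adherence outcome, because men who stop answering may also be men who take PrEP less regularly. The arms also differ in what participants receive. One gets 12 weeks of messages and the other a single emailed document, so the amount of loss and the reasons for it could differ by arm. Both examples of sensitivity analysis let observed men stand in for missing ones, so neither tests that assumption. The yes/no adherence responses in the app cannot fill the gap either, since they exist only in the intervention arm and have no baseline (SAP, Measures).

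**Working it through.** **Item count at T2** (all from SAP, Measures and Mediating Variables)

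- Adherence: 3 ("simple 3-item self-report adherence measure")
- Self-efficacy: 12 ("It is a 12-item scale of" confidence)
- Intention: 5 ("created a 5-item measure informed by a 2-item measure of safe sex intentions")
- Knowledge: 6 ("6-item multiple-choice instrument")
- Stress: 10 ("Stress burden will be assessed using the 10-item" scale)

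3 + 12 + 5 + 6 + 10 = 36. The primary outcome is 3/36 = 8.3% of the items.

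**The plan's own figure.** 92 × 1.20 = 110.4, which reproduces the stated 110. Dividing by the retained share instead gives 92 / (1 − 0.20) = 115, which does not.

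**Observed primary outcomes at the planned loss.** 110 × 0.20 = 22 missing; 110 − 22 = 88 observed; 92 − 88 = 4 short. Put another way, 110 can lose 110 − 92 = 18 men, or 18/110 = 16.4%, before the observed count falls below 92.

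**What a three-item fallback could recover.** Let r be the share of the 22 who would answer the three items. The documents give no value for r, so the full range is shown. Observed N = 88 + 22r.

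| r (assumed) | Observed N | Power on observed outcomes |
|---|---|---|
| 0 | 88 | 88–89% |
| 0.25 | 93.5 | 90–91% |
| 0.50 | 99 | 92% |
| 0.75 | 104.5 | 93–94% |
| 1 | 110 | 94–95% |

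Reaching 92 needs 4 of the 22, or 4/22 = 18%.

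The power column is illustrative. The plan states no numerical effect size, so the effect was solved back from 90% power at N = 92, with 4 predictors, two-sided alpha 0.05 and the noncentral F distribution (noncentrality f² × N, denominator degrees of freedom N − 5). That gives f² = 0.177 for the overall test of four predictors, or f² = 0.117 for the treatment coefficient alone. The column spans the two readings. It counts observed outcomes only, whereas the planned analysis would still include all 110 men through imputation.

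**The case against.** The plan does take steps to obtain T2. Every participant is contacted through two channels whatever his use of the app, and the T2 payment of $155 is far larger than the $20 for baseline. Nothing in the documents shows that 36 items cause men to break off, and the adherence items may already come first, since the SAP lists them first. A short form could also tempt some men to skip the mediator scales that Hypothesis 2 needs. All of this stands. It makes the point an inexpensive improvement and not an error, but it does not supply the missing fallback.

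Three stronger readings are tempting, and the documents do not support them.

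- *A reader might infer that a man who stops using the app has his outcome imputed.* Section 5.0 sends T2 to all participants, and the SAP disregards exposure. If he answers T2, his outcome is observed.
- *A reader might infer that exit is all-or-nothing.* Section 7.0 says only that "participants can excuse themselves from the study at any time with no negative repercussions". It does not say that stopping the app means leaving follow-up. The consent form, which may say more, is not among the documents reviewed.
- *A reader might infer that answered adherence items are overwritten when the rest of T2 is unfinished.* The imputation sentence quoted above could be read that way, but the SAP also says that it is missing T2 data that are imputed, and multiple imputation ordinarily leaves observed values alone. The text leaves partial T2 undefined; it does not state an overwriting rule.

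**Conclusion.** The point holds as a low-cost improvement in collecting the primary outcome. T2 carries 36 items, three of which matter for the primary analysis, and the plan has no route to those three alone before it imputes. At its own 20% loss the trial would observe 88 primary outcomes, 4 below its stated minimum. A fallback would raise this to somewhere between 88 and 110, depending on a response share that the documents do not give; 4 replies are enough to reach 92.

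The shortfall in observed numbers is modest. The main gain is that each reply removes one man from dependence on an untestable assumption. A reader might want to put a size on the resulting bias. The documents give neither missingness by arm nor the adherence of men who leave, so any figure would be assumed from start to finish, and none is offered here.

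**What to change.** 1. Protocol Section 5.0: place the three adherence items first in the T2 survey.
2. Protocol Section 5.0: after a fixed number of days (for example 7), send those three items alone, by text or email, to men in both arms who have not finished T2 and have not refused contact. Keep the delay short and record the date of the answer, because the items look back 30 days and a late reply covers a later window.
3. SAP, Data Analysis: define a partial T2. State that any answered adherence item is used as observed and that only missing items are imputed.
4. State outright what Section 5.0 and the SAP already imply: men who stop using the app are still sent T2.

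The cost is survey order, one automated message and a few sentences of protocol and SAP wording. The downside is that some men will give the primary outcome without the mediator data for Hypothesis 2. A partial payment may also be needed, since payment is currently described only after completion.
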